7.2 Control Group

1. On the day of surgery and prior to procedure, study patients will be waiting in the preoperative area.
2. The patient will be placed in bay #1 or other bay if #1 is not available in the preoperative area.
3. A member of the study personnel will assess the patient's baseline anxiety and pain.
4. The patient will undergo their surgical procedure.
5. The patient will be reevaluated for pain three times; when they arrive to the post-anesthesia recovery unit (PACU), after an hour, and after three hours.
6. The patient will be reevaluated for PONV/Impact score two times; after an hour from their arrival to the post-anesthesia recovery unit (PACU), and after 3 hours. Postoperative antiemetics used will also be collected from

- the patient's chart retrospectively, following enrollment.
7. Postoperative opioid consumption and anxiolytics used throughout hospitalization will be collected from the patient's chart retrospectively, following enrollment.
 8. Admission and discharge dates & times will be collected directly from the patient's chart retrospectively, following enrollment and used to determine total hospital length of stay.
 9. Patient satisfaction regarding surgery will be evaluated within a week after the discharge from the hospital.

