8.0 OUTCOME EVALUATION

All outcomes will be measured during the time periods illustrated in Table 1 using the following measurement methods:

- PreOP anxiety: Amsterdam Preoperative Anxiety and Information Scale (APAIS; Appendix I)
- State anxiety: Visual Analogue Score (VAS; Appendix VI) will be compared between pre and post acupuncture in the same patient within the acupuncture group.
- State anxiety: Visual Analogue Score (VAS; Appendix VI) preop anxiety assessment will be compared between the two groups to assess their baseline preop anxiety status on day of surgery.
- Pain: 11-point Numeric Pain Rating Scale (NPS; Appendix V) will be compared between the two groups
- Postoperative opioid consumption: collected through EPIC and converted into morphine milligram equivalents (MMEs) using Appendix IV. This will be compared between the two groups. Postoperative nausea and vomiting (PONV): PONV impact score (Appendix VII) will be compared between the two groups. Additionally, postoperative antiemetics needed during hospital admission will be collected directly from EPIC and compared between the two groups.
- Satisfaction with surgery: questionnaire (Appendix III) provided by a member of the study personnel by phone within a week after the discharge from the hospital.
- Adverse events related to the interventions will be recorded throughout enrollment.
- Anxiolytics medication needed throughout hospitalization will be collected directly from EPIC and compared between the two groups.
- Hospital length of stay will be collected directly from EPIC using hospital admission and discharge dates & times; this will be compared between the two groups.

Table 1. Outcome measurement time, researcher-to-patient interface, and method for all study outcomes.

[figure not shown]
Time	Interface	Outcome/ Measurement (Acupuncture)	Outcome/ Measurement (Control)
-10 to -7 days	PREPARE Center	
 • Preoperative anxiety/APAIS 	
 • Preoperative anxiety/APAIS

HHC-IRB
 IRB NUMBER: HHC-2021-0348
 IRB APPROVAL DATE: 06/02/2023

PreAQ/PreOP	Holding bay	
 • Anxiety/VAS • Pain/NPS • Anxiolytics 	
 • Anxiety/VAS • Pain/VAS • Anxiolytics
PostAQ/PreOP	Holding bay	
 • Anxiety/VAS • Pain/NPS 	NA

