PostOP	PACU: on arrival, 1 hour, and 3 hours	
 • Pain/NPS • Anxiolytics 	
 • Pain/NPS • Anxiolytics
PostOP	PACU: 1 hour, and 3 hours after arrival	
 • PONV/impact score 	
 • PONV/impact score
PO-Discharge	chart review	
 • Opioid use/MME • Anxiolytics • Antiemetics • Hospital length of stay 	
 • Opioid use/MME • Anxiolytics • Antiemetics • Hospital length of stay
Within a week from discharge	Phone call	
 • Satisfaction questionnaires 	
 • Satisfaction questionnaires

Abbreviations: NPS, numeric pain rating scale; PACU, post-anesthesia care unit; PONV, postoperative nausea and vomiting; POD, postoperative day.

Figure 3. Protocol schema.

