For the primary aim *pain*, based on data from the first 31 patients enrolled, our sample size calculation indicates that a minimum of 26 subjects per group are needed using a repeated measures design (each subject is measured 4 times) with 2 groups for a total of 52 subjects. This design achieves 81% power to test factor B1 if a Geisser-Greenhouse Corrected F Test is used with a 5% significance level and the actual effect standard deviation is 0.255 (an effect size of 0.40319). We estimate an attrition rate of 10%, which will require 58 subjects; however we will aim to enroll 60 subjects (30 per group). For the second primary aim *anxiety*, we performed two sample size calculations. One based on the data of all 17 patients in the acupuncture group, and another excluding the 3 patients for which protocol deviations were reported due to methods collecting the anxiety measure. With all 17 patients, the difference in the response of anxiety from pre to post acupuncture was normally distributed with a standard deviation 26.27. If the true difference in the mean response of matched pairs is 35.64, we will need to study 6 pairs of subjects to be able to reject the null hypothesis that this response difference is zero with probability (power) 0.8. The Type I error probability associated with this test of this null hypothesis is 0.05. With the 3 patients removed, the difference in the response of anxiety from pre to post acupuncture was normally distributed with standard deviation 26.588. If the true difference in the mean response of matched pairs is 39.14, we will need to study 6 pairs of subjects to be able to reject the null hypothesis that this response difference is zero with probability (power) 0.8. The Type I error probability associated with this test of this null hypothesis is 0.05.

Pain is the more appropriate primary outcome of the two primary outcomes to base the sample size on because there are 4 time points of data for each group for this variable. The other primary outcome, *anxiety* does not have a post measure for the control group (per the study design), and therefore a within-group pre to post change in the acupuncture group is being performed to examine this outcome. We acknowledge that this within group design is weaker than the design to assess the pain outcome measure.

Statistical Methods

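### Table 1 lists a pain VAS for controls before surgery, where Section 8.0 specifies the NPS for both arms; the two must be reconciled and the instrument actually used confirmed

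*Combined protocol and SAP*

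**What the plan says.** Section 8.0 opens with a list of measurement methods. For pain it states: "Pain: 11-point Numeric Pain Rating Scale (NPS; Appendix V) will be compared between the two groups". The only use that the list gives to the VAS is anxiety, for example: "State anxiety: Visual Analogue Score (VAS; Appendix VI) preop anxiety assessment will be compared between the two groups".

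Table 1 follows. In its PreAQ/PreOP row the acupuncture cell is "Anxiety/VAS • Pain/NPS • Anxiolytics" and the control cell is "Anxiety/VAS • Pain/VAS • Anxiolytics". Every other pain entry in the table is NPS. In the PACU row both arms have "Pain/NPS • Anxiolytics".

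Section 7.2 gives controls one assessment of "baseline anxiety and pain" before surgery. After surgery: "The patient will be reevaluated for pain three times" (PACU arrival, 1 hour, 3 hours). Neither 7.1 nor 7.2 names the pain instrument for the pre-operative step.

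Section 11.0 bases the sample size on pain because "there are 4 time points of data for each group for this variable". It specifies 26 patients per group, four measurements each, and 81% power.

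**The concern.** Table 1 is the only place that assigns an instrument by arm and by visit. A coordinator who works from it in the holding bay would hand controls a VAS for pain and acupuncture patients the NPS. The same control cell also calls for the anxiety VAS, so a VAS form would be to hand.

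The rating is part of the primary pain design. Controls have exactly 1 + 3 = 4 pain ratings, so for them the pre-operative rating must be one of the four time points. If the instruments differed, instrument and arm would be completely confounded at that time point, and no covariate could separate them. Any systematic difference between the scales would enter the pain model as a group or group-by-time effect, and the pre-operative comparison of pain between arms could not be interpreted.

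**Working it through.** **Inputs, all from Section 11.0 (Sample Size).** 26 per group; 4 ratings per patient; two-sided alpha 0.05; effect SD 0.255; effect size 0.40319; 10% attrition.

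**Step 1: reproduce the plan's figure.**
- With two equal groups, the group difference averaged over four ratings is 2 × 0.255 = 0.51 points.
- The SD of a patient's four-rating mean is 0.255 / 0.40319 = 0.6325.
- Between-group F test: df 1 and 2n − 2, noncentrality 2n × (effect size)². At n = 26 this is 52 × 0.40319² = 8.45, with df 1 and 50.
- Power is 81.4% (the plan states 81%). At n = 25 it is 79.8%, so 26 is the minimum for 80%.
- Attrition: 52 / 0.9 = 57.8, rounded up to 58, as stated.

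**Step 2: effect of an instrument offset.** Suppose the control pre-operative rating differs by b points from what the NPS would have given, with the SD unchanged. Only one of four ratings is affected, so the averaged group difference shifts by b/4. The noncentrality becomes 52 × (D / 2 / 0.6325)², where D is the resulting difference. The documents do not give b; 0.5 and 1 point are assumed.

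| Assumed b | Shift b/4 | Rejection rate with no true effect (D = b/4) | Power if the offset opposes the effect (D = 0.51 − b/4) |
|---|---|---|---|
| 0 | 0 | 5% | 81.4% (D = 0.51) |
| 0.5 | 0.125 | 10.8% | 57.6% (D = 0.385) |
| 1 | 0.25 | 28.7% | 30.7% (D = 0.26) |

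For b = 0.5 with no true effect, the noncentrality is 52 × (0.0625 / 0.6325)² = 0.51.

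**Step 3: if the pre-operative rating had to be dropped.** Assume a common within-patient correlation r (not given) and hold the four-rating SD at 0.6325. The single-rating SD is s = 0.6325 / √((1 + 3r)/4), and the SD of a three-rating mean is s × √((1 + 2r)/3). This is 0.730 at r = 0 and 0.639 at r = 0.8.
- Same average difference (0.51): power at 26 per group is 69.5% (r = 0) to 80.6% (r = 0.8). For 80% power, 34 to 26 per group are needed.
- Whole difference after surgery (0.51 × 4/3 = 0.68 on the three PACU ratings): power is 90.9% to 96.4%.

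**The case against.** The strongest answer is that this is a typing slip. Section 8.0 says which instrument measures pain, for both groups, and lists no pain VAS. The other pain cells in Table 1 are all NPS, and the stray entry sits directly after the anxiety VAS. That reading is the likelier one. It does not show which form controls were given, because the step lists in 7.1 and 7.2 are silent on the instrument.

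It is also fair that the stated objective is postoperative pain. The three PACU ratings are on the NPS in both arms, and the separate tests planned at those time points are untouched. Section 11.0 specifies no change-from-baseline analysis of pain. These points stand, and they limit the damage to the pre-operative comparison and the four-rating model.

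A reader might infer something much worse. The interim anxiety change of 35.64 cannot come from a 0–10 scale, so a pain VAS might also run 0–100, and a control with pain of 5 might be entered as 50. That would add (50 − 5)/4 = 11.25 points to the patient's four-rating mean, about 22 times the design difference of 0.51. The trial's own figures do not fit this. A shift of that size across controls would by itself give an effect SD near 11.25/2 = 5.6, whereas the first 31 patients gave 0.255, with an implied SD of 0.63. Unscaled 0–100 entries throughout the control arm are therefore not credible in the interim data. A VAS rescaled to 0–10 is not excluded.

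**Conclusion.** Table 1 and the Section 8.0 list contradict each other on the instrument for a primary outcome, and the discrepancy runs along the randomised arms. That much is certain. The documents do not establish that the arms were in fact measured differently, or that anyone intended this.

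The consequence is conditional on the cell having been followed. The four-rating group comparison would then carry an instrument effect of b/4. For an assumed offset of 0.5 to 1 point, the false-positive rate would be about 11% to 29% instead of 5%, or power about 58% to 31% instead of 81% if the offset opposes the effect. These figures rest on the assumed size of b, an unchanged SD, all controls being affected, and the between-group test used in the sample-size calculation.

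The PACU ratings are not affected. The stated sample size is not wrong on this account, and correcting the cell leaves it at 26 per group. The one thing still to confirm is that no VAS values lie behind the interim estimate. The point should be settled before analysis; how much it matters depends on the source check.

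**What to change.** 1. Change the control cell in the PreAQ/PreOP row of Table 1 to Pain/NPS, so that it agrees with Section 8.0.
2. Check the source forms for control pre-operative pain and record which instrument was used. Include the controls among the first 31 patients behind the re-estimate (31 − 17 = 14 controls).
3. Do not pool any VAS value with NPS values. If only a few controls are affected, treat those values as missing in the mixed model. If most or all are affected, that would empty the control pre-operative cell and make missingness depend on arm; in that case base the between-group model on the three PACU NPS ratings.

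The cost is one table cell and a review of forms. If the NPS was used throughout, nothing else changes. If not, some control pre-operative values are lost. At worst the comparison rests on three ratings, with power at 26 per group between 69.5% and 80.6% for the same average difference, and above 90% if the whole difference arises after surgery, under the correlation range assumed above.

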9.0 DATA MANAGEMENT

A Clinical Research Coordinator (CRC) will be assigned to the study. The responsibilities of the CRC will include project compliance, data collection, abstraction and entry, data reporting, regulatory monitoring, problem resolution and prioritization, and coordination of the activities of the protocol study team.

The data collected for this study will be entered into a database in an HHC-licensed version of REDCap. Source documentation will be available to support the computerized patient record and will be stored at the clinical anesthesia research office in a double-locked environment. All efforts will be made to ensure maintenance of patient confidentiality and HIPAA compliance. All data will be maintained on the REDCap database which will be stored on a secure HHC server and access will be protected by password. This database will only be accessible to the trained study personnel.

9.1 Quality Assurance

Monthly meetings will be conducted to monitor patient accruals and quality of data. Potential problems will be brought to the attention of the entire study team during the monthly meeting for discussion, action, and resolution.

At *approximately* 55-60% enrollment (14-15 per group depending on enrollment pace) point of the study, the research team will assess the accrued results in a planned interim analysis to determine whether any changes are necessary.

9.2 Data and Safety Monitoring

The study investigators will be responsible for the safety of the study participants, and they will stress the importance of reporting adverse events to the participants. Investigators will also consistently monitor each participant for adverse events. Adverse events, related or unrelated to the acupuncture procedure, will be reported, attributed, and graded for severity by the clinician and documented in EPIC. Serious adverse events or unanticipated problems will be reported to the IRB.

10.0 PROTECTION OF HUMAN SUBJECTS

Every effort will be made to ensure the safety of our patients and the confidentiality of their medical information. During the enrollment and consent process, all risks, benefits, side effects, and alternatives will be discussed. Also, it will be stressed that this is a voluntary study and that the patient can withdraw without prejudice at any time.

Benefits

The potential benefit of this study is that preoperative acupuncture is effective in reducing preoperative anxiety and postoperative pain in patients undergoing lower extremity total joint arthroplasty. Such a reduction in postoperative pain and anxiety could potentially increase overall patient satisfaction. Further, patients will not be compensated for participating in this study, but they will receive the acupuncture service at no cost.

Risks

The risks of participation include the risks associated with performing acupuncture include, but are not limited to, the following: minor bleeding, pain, pneumothorax, abdominal injuries, heart injuries, CNS injuries, neck injuries, eye injuries, peripheral nerve injuries, and infection.

Alternatives

The alternative to acupuncture for addressing high-anxiety patients is the standard of care. For pain, this includes the use of standard pain medications, including opioid and non-opioid analgesics, in addition to regional blocks. For anxiety, this includes the regular use of anxiolytic medications and psychological consultation referrals. These standard-of-care procedures will not be replaced by acupuncture and rather performed in adjunct. A patient's decision on whether or not to participate in this study will not affect the availability of standard and supportive measures.

Costs

There will be no additional cost incurred by the participant to participate in the study.

Acupuncture materials and service will be provided at no additional cost to the patients enrolled in the study and will be provided by one of the study investigators.

Voluntary Nature of Study

Participation in this study is entirely voluntary. Patients will be informed of the extent of the risks, benefits, adverse events, alternatives/options for treatment, financial costs/burdens, and the voluntary nature of the study. The responsible investigator will ensure that this study is conducted in agreement with the Declaration of Helsinki (Tokyo, Venice, Hong Kong, Somerset West, and Edinburgh amendments). The study will seek in every way to protect the rights of human subjects. No patient will be required to participate in the study, and participation or lack of participation will not affect the patient's subsequent care or treatment.

Participation will be entirely voluntary and subjects will not be reimbursed for participation in the study. Throughout the study, patient confidentiality will be maintained. No results of the study will be presented or discussed in a fashion that will allow identification of a particular patient in the study. All adverse events will be fully disclosed to the IRB in a timely fashion as required.

10.1 Privacy

HHC's Privacy Office may allow the use and disclosure of protected health information pursuant to a completed and signed Research Authorization form. The use and disclosure of protected health information will be limited to the individuals described in the Research Authorization form. A Research Authorization form must be completed by the Principal Investigator and approved by the IRB and HRPP (IRB/HRPP).

10.2 Adverse Events

The incidence and severity of adverse events is highly dependent on the experience and skill of the practitioner, and when provided by a physician, acupuncture is accepted as a safe treatment.^[29,36,37] Acupuncture-related adverse events occur in about 6% of cases; the vast majority of these are usually minor and most commonly include bleeding, discomfort, and residual pain at the insertion points.^[36] Serious acupuncture-related adverse events occur in just 0.024% of cases.^[37] Of these, the most frequently cited include: pneumothorax, abdominal injuries, heart injuries, CNS injuries, neck injuries, eye injuries, peripheral nerve injuries, and infection.^[37] Though acupuncture-related deaths have been reported, the incidence is statistically negligible, and even surveys covering more than 3 million acupuncture treatments report no cases of death.^[38]

Adverse events will be monitored during and after acupuncture and throughout admission. Events will be recorded as safety measures. Emergency visits and hospital readmissions stated in EPIC will be recorded up to thirty days postoperatively.

10.3 Serious Adverse Event (SAE) Reporting

The risks associated with acupuncture are viewed as minimal risk. Although we have assessed the proposed study as one of minimal risk, the potential exists for anticipated and/or unanticipated adverse events, serious or otherwise, to occur since it is not possible to predict with certainty the absolute risk of this procedure in this context.

Therefore, we provide a plan for monitoring the safety of the participants in the study as

follows:

Attribution of Adverse Events

Adverse events will be monitored for each subject participating in the study and attributed to the study procedures / design by the principal investigator according to the following categories:

- Definite: Adverse event is clearly related to investigational procedures(s)/agent(s)
- Probable: Adverse event is likely related to investigational procedures(s)/agent(s)
- Possible: Adverse event may be related to investigational procedures(s)/agent(s)
- Unlikely: Adverse event is likely not to be related to the investigational procedures(s)/agent(s)
- Unrelated: Adverse event is clearly not related to investigational procedures(s)/agent(s)

Grading Adverse Events

The following scale will be used in grading the severity of adverse events noted during the study:

1. Mild adverse event
2. Moderate adverse event
3. Severe adverse event

An adverse event is considered serious if it results in ANY of the following outcomes:

- Death
- A life-threatening adverse event
- An adverse event that results in inpatient hospitalization or prolongation of existing hospitalization
- A persistent or significant incapacity or substantial disruption of the ability to conduct normal life functions
- A congenital anomaly/birth defect
- Important Medical Events (IME) that may not result in death, be life threatening, or require hospitalization may be considered serious when, based upon medical judgment, they may jeopardize the patient or subject and may require medical or surgical intervention to prevent one of the outcomes listed in this definition

Note: hospital admission for a planned procedure/disease treatment is not considered an SAE. Additionally, grade 1-3 events from the following list of protocol complications will be considered expected on study and not reportable as SAEs: bleeding, discomfort, and residual pain at the insertion points. These will be tracked separately through the protocol data collection sheets.

SAE reporting is required as soon as the participant signs consent. SAE reporting is required for 30 days after the participant's last investigational treatment or intervention. If an SAE requires submission to the IRB office per IRB SOP, the SAE report must be sent to the IRB within 5 calendar days of the event. The IRB requires submitting the SAE electronically using iRIS. A copy of the SAE report should be retained in the patient's study chart for auditing purposes. The report should contain the following information: subject's initials, medical record number, protocol number, and title. The

HHC-IRB

IRB NUMBER: HHC-2021-0348

IRB APPROVAL DATE: 06/02/2023

PI's signature and the date it was signed are required on the completed report.

Data to be entered for SAEs:

- The date the adverse event occurred
- The adverse event
- The grade of the event
- Relationship of the adverse event to the treatment (drug, device, or intervention)
- If the AE was expected
- The severity of the AE
- The intervention
- Detailed text that includes the following
 - An explanation of how the AE was handled
 - A description of the subject's condition
 - Indication if the subject remains on the study
- If an amendment will need to be made to the protocol and/or consentform
- If the SAE is an Unanticipated Problem

Reporting Adverse Events to Investigators

For the current study, all investigators listed on the protocol will be notified, and the principal investigator will conduct a review of all adverse events upon completion of every study subject. The principal investigator will evaluate the frequency and severity of the adverse events and determine if modifications to the protocol or consent form are required.

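### The Note in 10.3 exempts three kinds of needle-site event from SAE reporting at every grade on the protocol's scale, with no exception for an event that meets a seriousness outcome

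*Combined protocol and SAP*

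**What the plan says.** Section 10.3 sets out three things in sequence.

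- **A severity scale.** It is introduced with "The following scale will be used in grading the severity of adverse events noted during the study". It has three levels: 1 is mild, 2 is moderate, and the top level is "3. Severe adverse event".
- **A definition of seriousness by outcome.** "An adverse event is considered serious if it results in ANY of the following outcomes". Six outcomes follow. One of them is "An adverse event that results in inpatient hospitalization or prolongation of existing hospitalization".
- **A Note after that list.** Planned admissions are first said not to count as SAEs. Then, for bleeding, discomfort and residual pain at the needle sites, "grade 1-3 events from the following list of protocol complications will be considered expected on study and not reportable as SAEs". The Note adds: "These will be tracked separately through the protocol data collection sheets".

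Two general statements appear elsewhere. Section 9.2 says "Serious adverse events or unanticipated problems will be reported to the IRB". Section 10.0, under the voluntary nature of the study, says "All adverse events will be fully disclosed to the IRB in a timely fashion as required". The rest of 10.3 requires an SAE report to reach the IRB within 5 calendar days, but only where the IRB SOP calls for submission.

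**The concern.** A limit written as grades 1 to 3 suggests that some higher grade stays reportable. On this protocol's scale there is none. The limit looks like a safeguard but does no work.

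The larger difficulty is that the Note decides reportability by event type and severity grade, whereas the protocol defines seriousness by outcome. Severity and seriousness are different properties: a moderate event can lengthen a hospital stay, and a severe one may have no listed outcome. Without wording that gives way to the seriousness list, the Note takes some events that are serious by the protocol's definition out of SAE reporting.

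At stake is the handling of safety reports. Safety is part of the secondary objective in 1.0, so the rule for what is reported as serious should give the result its authors meant. No efficacy endpoint, sample size, power or type I error is affected.

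**Working it through.** No figure in the plan needs to be reproduced. The check is a count of grades and a reading of the sections together.

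**1. Grades defined against grades exempted (10.3).**

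| | Grade 1 | Grade 2 | Grade 3 | Higher |
|---|---|---|---|---|
| Defined on the scale | yes | yes | yes | none |
| Exempted by the Note | yes | yes | yes | not mentioned |

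Grades still reportable for these three event types: 3 − 3 = 0. The data fields for an SAE list grade and severity as separate entries, but 10.3 supplies no second scale that could give a higher grade.

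**2. One hypothetical event taken through the rules.** Suppose needle-site bleeding lengthens the patient's hospital stay.

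- Grade: it must be 1, 2 or 3, because nothing else is defined.
- Seriousness: it meets a listed outcome, and any one outcome is enough, so it is serious.
- Note: the event type is on the exempt list and the grade lies in the exempt range, so it is not reportable as an SAE.

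The second and third results do not fit together, and 10.3 does not say how to resolve them.

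**3. Does any other text restore reporting?**

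- Section 9.2 is a general statement. It does not say that it prevails over the Note.
- The disclosure sentence in 10.0 is qualified by what is required, so it does not settle the matter.
- The 5-calendar-day rule applies to an SAE that the IRB SOP says must be submitted. It does not clearly reach an event that the Note has made not reportable as an SAE.
- Expectedness does not explain the exemption. Whether the event was expected is one of the items to be entered for an SAE, so an SAE can be an expected event.

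None of these supplies the missing exception.

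**4. Is the event lost?** No. Adverse events are graded and documented in EPIC (9.2). The exempted types are tracked on the data collection sheets, and the principal investigator reviews all adverse events after each subject completes (both 10.3). Length of stay (8.0) and readmissions up to thirty days after surgery (10.2) are also collected.

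**5. Reach of the exemption.** I read the needle-site qualifier as applying to all three event types, which matches the description of common minor events in 10.2. If it applied to residual pain alone, the exemption for bleeding and discomfort would be wider still. All other event types, including infection and nerve injury, stay outside the Note.

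**The case against.** The strongest reply is that the Note is a deliberate, specific exception for trivial events. Section 10.2 describes the vast majority of acupuncture-related events as minor. The needles are 13 mm by 0.20 mm, placed at ear and wrist points for about 20 minutes (3.3, 3.4). Patients with an INR above 1.5, a platelet count below 70,000, active coagulopathy or anticoagulant use that raises bleeding risk are excluded (4.2). Capture is intact, and the pages carry an IRB approval stamp.

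Most of this stands, and it is why the point is minor. It does not cure the wording, because the Note expressly reaches grade 3. If only trivial events were meant, the correction simply says so. It could also be argued that a fatal or life-threatening event lies above grade 3. The text does not say that. Even if it did, the other four listed outcomes, including hospitalization, would still be covered by the exemption.

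Some stronger readings are tempting but are not supported:

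- *The Note strips these events of SAE status.* The Note says planned admissions are not considered SAEs, but says only that the needle-site events are not reportable as SAEs. Reportability is affected; classification is not clearly changed.
- *The Note flatly contradicts 9.2.* A general statement can be qualified by a later, specific exception, and the SOP condition in 10.3 already qualifies it. The defect is the missing exception within 10.3.
- *Calling the events expected closes the unanticipated-problem route to the IRB.* The documents do not define an unanticipated problem, and 10.3 records expectedness and unanticipated-problem status as separate items.
- *The 0.024% serious-event rate in 10.2 measures the problem.* The serious types that section cites most often do not include the three exempted ones, so the rate mostly describes events the Note does not touch.

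**Conclusion.** The Note is wrong as written, in a minor way. Its grade limit covers the whole of the protocol's scale, and it lacks an exception for events that meet a listed seriousness outcome. An event that is serious under the protocol's own definition could therefore go unreported as an SAE.

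The effect is confined to SAE reporting of three local event types, which would still be recorded and reviewed as adverse events. Such cases should be very rare. The documents give no serious-event rate for these types, so no number can be attached. Whether any IRB report would be lost depends on the IRB SOP, which the documents do not include.

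Confidence is high that the wording gap exists. It does not extend to any claim of practical harm. The conclusion assumes that the three-level scale is the one the Note refers to; no other is defined.

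**What to change.** Reconcile the Note with the seriousness definition in 10.3. State that the exemption covers only needle-site bleeding, discomfort or residual pain that meets none of the listed seriousness outcomes, whatever its grade. The reference to grades 1 to 3 then becomes unnecessary and can be removed.

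The cost is one sentence in the protocol and negligible extra reporting. No visit, dataset or analysis changes.
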